5.2 Data processing

Data processing, controls of plausibility and query handling will be carried out by the [REDACTED] [REDACTED]. The study database will be created according to the format and content of the eCRF and the CIP. The ICD-10 code will be used for coding of adverse events and previous / concomitant diseases.

Clinical Investigation Plan

CIP Reference No.:2018-GI (OEKG) -01. The **SAMISEN** study - Final Version 02 - Date 23th April 2019

6 AMENDMENTS TO THE CIP

CIP amendments or supplements (apart from minor administrative changes) require a written amendment. Amendments must be approved by the EC and the regulatory authorities, if locally applicable, before implementation. A copy of the written approvals will be provided to the investigators.

The following list provide an overview about the changes compare to CIP version no. 01 from 20. December 2018.

Table 3 List of changes CIP version 01 versus CIP version 02.

Amend- ment no. 01	Section	Previous version CIP version 01 from 20 th Dec 2018	Changed Version CIP version 02 from 23 April 2019
	Trial summary / endpoints	
Endpoints
 
....
 
 • Endoscopic and ERCP success rates in patients with altered upper GI anatomy (e.g. Roux-en-Y gastric bypass). 	
Endpoints
 
....
 
 • Endoscopic success rates.
	Trial summary/ study Population	
Inclusion criteria
 
 1. Signed informed consent 2. Patients with small bowel disease indicated for deep enteroscopy, including but not limited to: 
 • Gastrointestinal bleeding • Crohn's disease • Abdominal pain or chronic diarrhea • Large polyps (>10–15mm) in the jejunum and ileum in patients with Peutz–Jeghers syndrome • Nonresponsive or refractory coeliac disease • Results and hints from other preliminary investigations, e.g. small-bowel capsule endoscopy, small-bowel imaging examinations etc. which warrant further work-up with antegrade and/or retrograde enteroscopy of the small-bowel. 
or
 
 • Patients with altered upper GI anatomy (e.g. Roux-en-Y or BII) indicated for 	
Inclusion criteria
 
 1. Signed informed consent 2. Patients with small bowel disease indicated for deep enteroscopy, including but not limited to: 
 • Gastrointestinal bleeding • Crohn's disease • Abdominal pain or chronic diarrhea • Large polyps (>10–15mm) in the jejunum and ileum in patients with Peutz–Jeghers syndrome • Nonresponsive or refractory coeliac disease • Results and hints from other preliminary investigations, e.g. small-bowel capsule endoscopy, small-bowel imaging examinations etc. which warrant further work-up with antegrade and/or retrograde enteroscopy of the small-bowel.

Clinical Investigation Plan

CIP Reference No.:2018-GI (OEKG) -01. The **SAMISEN** study - Final Version 02 - Date 23th April 2019

		ERCP where access with conventional ERCP devices is of no avail and after careful individual risk assessment	
1 BACKGRO UND AND RATIONAL E	
Small bowel enteroscopy is usually performed in order to evaluate gastrointestinal bleeding, small bowel tumors, polyps, inflammatory or other small bowel diseases. Video capsule endoscopy, single- (SBE), double-balloon (DBE) or spiral enteroscopy are the most popular non-surgical endoscopic techniques in this context. Hereof the endoscopic approach offers additional diagnostic and therapeutic options as biopsies and direct therapeutic intervention is possible compared to capsule endoscopy. These enteroscopy systems – also called overtube-assisted enteroscopy (OAE) techniques - are used to visualize the small-bowel and proceed with a therapeutic intervention, either during the same or in a subsequent session. For example the DBE utilizes distal and proximal balloons that can be inflated and deflated to “anchor” and move the bowel, thereby assisting the operator in advancing the endoscope while gathering the bowel onto the overtube shaft.
 
However, the SBE and DBE procedures are time consuming and usually require 2 operators to perform this kind of examination.
 
Patients with altered upper gastrointestinal (upper GI) anatomy (such as Roux-en-Y gastric bypass) indicated for endoscopic retrograde cholangiopancreatography (ERCP) represent a special challenge to the investigator. The new endoscopic techniques originally designed for deep enteroscopy have increased the potential to reach the area of interest and successfully perform ERCP and therapeutic interventions at acceptable complication rates (Skinner et al. 2014). This has led to increasing acceptance of OAE techniques in this special patient cohort.
	
Small bowel enteroscopy is usually performed in order to evaluate gastrointestinal bleeding, small bowel tumors, polyps, inflammatory or other small bowel diseases. Video capsule endoscopy, single- (SBE), double-balloon (DBE) or spiral enteroscopy are the most popular non-surgical endoscopic techniques in this context. Hereof the endoscopic approach offers additional diagnostic and therapeutic options as biopsies and direct therapeutic intervention is possible compared to capsule endoscopy. These enteroscopy systems – also called overtube-assisted enteroscopy (OAE) techniques - are used to visualize the small-bowel and proceed with a therapeutic intervention, either during the same or in a subsequent session. For example, the DBE utilizes distal and proximal balloons that can be inflated and deflated to “anchor” and move the bowel, thereby assisting the operator in advancing the endoscope while gathering the bowel onto the overtube shaft.
 
However, the SBE and DBE procedures are time consuming and usually require 2 operators to perform this kind of examination.
	
1.2. Justification for the	...	For the same reason inclusion criteria are kept as broad as possible. For the same reason inclusion criteria are kept as broad as possible. In

Clinical Investigation Plan

CIP Reference No.:2018-GI (OEKG) -01. The **SAMISEN** study - Final Version 02 - Date 23th April 2019

Design of the Clinical Investigation	
In summary all patients are eligible where the physician realizes an indication for deep enteroscopy for further diagnostic or therapeutic work up. In patients with altered upper GI anatomy, such as e.g. Roux-en-Y gastric bypass indicated for ERCP is in line with the intended use and hence can be performed using PowerSpiral if deemed appropriate by the investigator. So inclusion of these patients into this registry is possible. The exclusion criteria will only affect patients under the age of 18 years and pregnant women. Otherwise clinical judgement of the treating physician is the only relevant and leading reason for exclusion. Of course giving signed informed consent by all study subjects is a prerequisite for participation in this "registry".
	
summary all patients are eligible where the physician realizes an indication for deep enteroscopy for further diagnostic or therapeutic work up. The exclusion criteria will only affect patients under the age of 18 years and pregnant women. Otherwise clinical judgement of the treating physician is the only relevant and leading reason for exclusion. Of course giving signed informed consent by all study subjects is a prerequisite for participation in this "registry".

3.1.3 Variables in the Clinical Investigation	
.....
 
 • Total small bowel enteroscopy rate: Defined as complete evaluation of the small bowel either with a single approach or combined anterograde and retrograde approach (if complete small bowel enteroscopy is intended anyway (Committee et al. 2015; Gerson et al. 2015). • User feedback and judgment of handling characteristics and other aspects. • For "ERCP patients" ²only: 
 ○ Endoscopic Success Rate: defined as the percentage of procedures in which the investigator was able to reach the major papilla or the biliodigestive or pancreatic anastomosis when ERCP was planned. ○ ERCP Success Rate: defined as the 	
.....
 
 • Total small bowel enteroscopy rate: Defined as complete evaluation of the small bowel either with a single approach or combined anterograde and retrograde approach (if complete small bowel enteroscopy is intended anyway (Committee et al. 2015; Gerson et al. 2015). • User feedback and judgment of handling characteristics and other aspects.

² Patients with altered upper GI anatomy now indicated for ERCP with PowerSpiral as judged by the investigator

Clinical Investigation Plan

CIP Reference No.:2018-GI (OEKG) -01. The **SAMISEN** study - Final Version 02 - Date 23th April 2019

		
percentage of therapeutic interventions successfully completed by the investigator.
 
 ○ Total procedure time, safety related aspects and user feedback will be collected as described above. 	
	3.3.1 Inclusion criteria	
In order to be considered eligible for participation in this investigation subjects must meet all of the inclusion criteria listed below:
 
 • Signed informed consent • Patients with small bowel disease indicated for deep enteroscopy, including but not limited to: 
 • Gastrointestinal bleeding • Crohn's disease • Abdominal pain or chronic diarrhea • Large polyps (>10–15mm) in the jejunum and ileum in patients with Peutz–Jeghers syndrome • Nonresponsive or refractory coeliac disease • Results and hints from other preliminary investigations, e.g. small-bowel capsule endoscopy, small-bowel imaging examinations etc. which warrant further work-up with antegrade and/or retrograde enteroscopy of 	
In order to be considered eligible for participation in this investigation subjects must meet all of the inclusion criteria listed below:
 
 • Signed informed consent • Patients with small bowel disease indicated for deep enteroscopy, including but not limited to: 
 • Gastrointestinal bleeding • Crohn's disease • Abdominal pain or chronic diarrhea • Large polyps (>10–15mm) in the jejunum and ileum in patients with Peutz–Jeghers syndrome • Nonresponsive or refractory coeliac disease • Results and hints from other preliminary investigations, e.g. small-bowel capsule endoscopy, small-bowel imaging examinations etc. which warrant further work-up with antegrade and/or retrograde enteroscopy of the small-bowel.

Clinical Investigation Plan

CIP Reference No.:2018-GI (OEKG) -01. The **SAMISEN** study - Final Version 02 - Date 23th April 2019

		
the small-bowel. or
 
 • Patients with altered upper GI anatomy (e.g. Roux-en-Y or BII) indicated for ERCP where access with conventional ERCP devices is of no avail and after careful individual risk assessment 	
3.4.2 Description of clinical investigation related procedures and assessed data	At visit V2 and V3 (optional):	At visit V2 and V3 (optional): At this visit the PowerSpiral enteroscopy will be performed.	
4.1.2 Efficacy evaluation	
 • For "ERCP patients" only: 
 ○ Endoscopic Success Rate: defined as the percentage of procedures in which the investigator was able to reach the major papilla or the biliodigestive or pancreatic anastomosis when ERPC was planned. ○ ERCP Success Rate: defined as the percentage of therapeutic interventions successfully completed by the investigator ○ Total procedure time, safety related aspects and user feedback will be collected as 	-/-	

Clinical Investigation Plan

CIP Reference No.:2018-GI (OEKG) -01. The **SAMISEN** study - Final Version 02 - Date 23th April 2019

		described above	
4.2 Subgroup Analyses		Patients indicated for ERCP with PS will be analyzed separately.	No subgroup analysis planned.
7.1. CIP deviation		
Major CIP deviations are, but are not restricted to
 
• Deviation from the in- and exclusion criteria• Performing ERCP before the individual learning curve (5 PS procedures performed as deep enteroscopy) has been completed.	
Major CIP deviations are, but are not restricted to
 
• Deviation from the in- and exclusion criteria

Clinical Investigation Plan

CIP Reference No.:2018-GI (OEKG) -01. The **SAMISEN** study - Final Version 02 - Date 23th April 2019

7 CIP DEVIATIONS

The investigator must not deviate from the procedures described in this CIP.

Under emergency circumstances, deviations from the CIP to protect the rights, safety and well-being of human subjects may proceed without prior approval of the sponsor and the EC. Such deviations must be documented and reported to the sponsor and the EC as soon as possible.

Classifications into minor and major CIP deviations will be performed by the clinical operations manager and statistician at the end of the study.

Major CIP deviations are, but are not restricted to

- Deviation from the in- and exclusion criteria

Clinical Investigation Plan

CIP Reference No.:2018-GI (OEKG) -01. The **SAMISEN** study - Final Version 02 - Date 23th April 2019

8 DEVICE ACCOUNTABILITY

This study is a post-market study. The PS enteroscopes are CE-marked. Hence from a regulatory perspective strict device accountability is not needed. However, the sponsor will have a list of serial numbers and can track which device was delivered to which study site.

The devices are usually purchased by the site. Olympus will provide devices as loaner equipment to a limited number of sites serving as centers of excellence. Any loaner equipment shall be exclusively used for the examination of study patients. After reaching the agreed quota per site (5 learning curve patients per investigator + 22 subjects counting towards the endpoints) the device must be returned to Olympus. Details are specified in the Clinical Trial Agreements.

Clinical Investigation Plan

CIP Reference No.:2018-GI (OEKG) -01. The **SAMISEN** study - Final Version 02 - Date 23th April 2019

9 STATEMENT OF COMPLIANCE

9.1 Ethical and Regulatory Aspects

The clinical investigation will be carried out in accordance with the following texts:

- The Declaration of Helsinki (1996)
- Good Clinical Practice (ICH E6) (current version)
- DIN EN ISO 14155:2011

The clinical investigation will not begin until the required approval / favorable opinion from the EC and / or regulatory authority (if applicable) have been obtained. Any additional requirements imposed by the EC or regulatory authority will be followed.

Regulatory reporting responsibilities are specified in the respective Clinical Trial Agreements that also need to be duly signed prior to the first enrollment.

Quality Control and Quality Assurance systems will ensure that the clinical investigation is conducted according to local law and Good Clinical Practices. Olympus Europa SE & Co. KG will follow their own Standardized Operating Procedures covering all aspects of the clinical investigation.

9.2 Patient Coverage

The PowerSpiral medical device is a CE-certified and CE-marked product. Any patient product liability claims will be covered in accordance with the applicable product liability law. Additional patient coverage will be provided by the sponsor if required by national law.

9.3 Retention of Documents

The investigator must conduct the study in compliance with the Medical Devices Act and Good Clinical Practices. The study documents comprise the following:

- Case report forms,
- Data correction/clarification forms,
- Source documents,
- Correspondence between sponsor/CRO and investigator,
- Regulatory documents such as:
 - Signed CIP and any amendments,
 - EC approval and correspondence,
 - Curriculum Vitae of medical personnel (investigators, study nurses, etc.),
 - Subject signed consent forms,

Clinical Investigation Plan

CIP Reference No.:2018-GI (OEKG) -01. The **SAMISEN** study - Final Version 02 - Date 23th April 2019

- Investigator's contract

Source documents for study subjects shall be marked with the CIP Reference number **[2018-GI (OEKG) -01]**.

The CIP, case report forms, correspondence, original informed consent forms, subject identification log with names of the patients and other documents concerning the study must be kept by the investigator in the investigator site file according to local regulations. The safekeeping period is usually 15 years after study close-out.

9.4 Auditing procedures

National or foreign Health authorities may want to inspect your site at any time during or after the study. By participating in this clinical investigation investigators agree to and will grant authorized inspectors access to all original documents, including subject files. If subject files or medical records are stored on a computer system, the investigator (or delegate) shall ensure that data requested by the inspector is printed on paper, dated and signed before handed over to the inspector. Inspectors do not have direct access to the sites computer system.

Also the sponsor (Olympus Europa SE & Co. KG) reserves the right to perform an audit during the active study phase or after study closeout.

Clinical Investigation Plan

CIP Reference No.:2018-GI (OEKG) -01. The **SAMISEN** study - Final Version 02 - Date 23th April 2019

10 INFORMED CONSENT

Before enrolment in the clinical investigation, the investigator must make sure that all eligible subjects are well provided with detailed information, both orally and in writing, about the following points in particular:

- Aims, duration and methods of the clinical investigation.
- Risks, anticipated benefits and potential hazards according to current knowledge.
- That he/she is free to withdraw his/her consent at any time without affecting subsequent treatment or his/her relation to the physician.
- That the clinical research monitors and auditors, Health Authority Inspectors and EC/IRB members may have access to their clinical source data.

Informed consent must be given by a standard written declaration drafted in simple non-technical language. Subjects will also be informed that the data collected during the study will be archived and processed in accordance with local individual data protection law.

The subject must read and understand the contents of this form before signing and dating it. He/she has to be provided with a signed version. No subject may be enrolled in this clinical investigation before giving his/her informed consent in writing.

The investigator will inform all subjects included in the clinical investigation about any new information on the investigational device discovered during the study, in accordance with the recommendations of Olympus Europa SE & Co. KG, the sponsor, and the EC.

The investigator must hold an updated list of all subjects enrolled in the study by recording their subject number. A Subject Identification Log Template will be provided by the sponsor.

Clinical Investigation Plan

CIP Reference No.:2018-GI (OEKG) -01. The **SAMISEN** study - Final Version 02 - Date 23th April 2019

11 ADVERSE EVENTS, ADVERSE DEVICE EFFECTS AND DEVICE DEFICIENCIES

11.1 Definitions (according to ISO 14155:2011)

11.1.1 Adverse event (AE)

The term AE describes any untoward medical occurrence, unintended disease or injury, or untoward clinical signs (including laboratory values) in subjects, users or other persons, whether or not related to the investigational medical device. For subjects this definition includes:

- Events related to the investigational medical device
- Events related to the procedures involved
- For users or other persons, this definition is restricted to events related to investigational medical devices

Note:

A “significant deterioration in laboratory parameters” means an abnormal lab value, which is deemed clinically significant when any of the following conditions is met:

- The abnormality suggests a disease and/or organ toxicity that is new or has worsened from baseline.
- The abnormality is of a degree that requires additional active management, e.g. change of treatment, discontinuation of treatment, close observation, more frequent follow-up assessments, or further diagnostic investigation.

Therefore, a clinically significant deterioration of a lab value is one that indicates a new disease process, worsening of an existing condition, or requires further action(s) to be taken.

11.1.2 Adverse Device Effect (ADE)

An ADE is an adverse event related to the use of an investigational medical device.

Note:

- This definition includes any adverse event resulting from insufficiencies or inadequacies in the instructions for use, the deployment, the implantation, the installation, the operation, or any malfunction of the investigational medical device.
- This definition includes any event that is a result of a use error or intentional misuse.
- This includes medical devices already on the market that are being evaluated for unintended uses, new populations, new materials or design changes.

Clinical Investigation Plan

CIP Reference No.:2018-GI (OEKG) -01. The **SAMISEN** study - Final Version 02 - Date 23th April 2019

11.1.3 **Serious Adverse Event / Serious Adverse Device Effect (SAE /SADE)**

A SAE/SADE is further specified by the fact that it results or could have resulted in death or severe deterioration of health of a subject, user, or other persons, whether (SADE) or not (SAE) related to the investigational medical device.

The criteria for a Serious Adverse Event (SAE) are the following:

- Led to a death,
- Led to a serious deterioration in health of the subject, that either resulted in:
 - A life-threatening illness or injury, or
 - A permanent impairment of a body structure or a body function, or
 - In-patient or prolonged hospitalization, or
 - In medical or surgical intervention to prevent life threatening illness or injury or permanent impairment to a body structure or a body function,
- Led to fetal distress, fetal death or a congenital abnormality or birth defect.

Note: Planned hospitalization for a pre-existing condition, or a procedure required by the CIP, without serious deterioration in health, is not considered a serious adverse event.

The following points should be taken into account when evaluating the seriousness of an Adverse Event:

- The life-threatening criterion indicates that there was an immediate risk of death at the time of its occurrence. This does not mean that if the adverse event had occurred in a more severe form it would have led to death.
- The following events are not considered to be serious adverse events:
 - An event causing a brief visit to a hospital consultation, an open-door or day hospital.
 - Outpatient treatment in the emergency department although the reason for which this treatment was instituted may be serious.
 - Admission to hospital (more than one night in a hospital bed) including surgical operations planned before or during the study if the condition was present before the study and provided that it does not worsen during the study.

Note:

A state of pregnancy is an exclusion criterion. Hence contraceptive measures must be taken by all subjects of childbearing potential throughout the study. However, if pregnancy is discovered during the study, the study participation must be discontinued immediately and the outcome of the pregnancy must be followed up carefully. Any abnormal outcome of the child or the mother must be documented.

Clinical Investigation Plan

CIP Reference No.:2018-GI (OEKG) -01. The **SAMISEN** study - Final Version 02 - Date 23th April 2019

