3.4.3 Study Visits Schedule

After visit V1 the investigator will schedule the antegrade or retrograde or combined enteroscopy depending on investigator's discretion. There are no predetermined time intervals between V1 and V2 or V2 and V3. Also the standard preparation procedure in your hospital for defecation before small-bowel enteroscopy shall be followed as usual.

The small-bowel enteroscopy duration depends on the individual diagnostic and treatment activities for each patient. Approximately 45 min are assumed for an uncomplicated antegrade examination.

The final visit V4 shall be completed prior to hospital discharge.

Premature study discontinuation of a study subject is to be noted as such on the case report form (eCRF).

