2.2 Flow chart of study activities

2.3 Study Objectives

The primary endpoint of this study is the assessment of the rate of serious adverse events to show a non-inferiority to preceding generations of balloon assisted enteroscopes. Thus, the observed rate of serious adverse events will be computed alongside it's 95% Clopper-Pearson confidence interval. If the upper confidence limit will be 8% or less, non-inferiority will be concluded.

Secondary objectives are the description of the following parameters:

- Reaching the anatomical region of interest
- Therapeutic yield
- Total procedure time
- Total small bowel enteroscopy rate
- User feedback
- Safety profile
- Effect of the learning curve

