2.4 Primary and secondary variables

Primary efficacy variable:

The rate of serious adverse events during and after enteroscopy will constitute the primary endpoint for this study.

Secondary efficacy variables:

- Reaching the anatomical region of interest: The rate of successfully reaching the suspected anatomical target region (either by antegrade or by retrograde route) compared to all attempts represents the endpoint 'anatomical success rate'.
- Therapeutic yield: Defined as the percentage of patients with any endoscopic intervention / therapy with the exception of biopsies. (Sethi et al. 2014; Prachayakul et al. 2013; Sanaka et al. 2012)
- Total procedure time: Period in minutes needed to complete the procedure.
- Total therapeutic intervention time: Period in minutes dedicated to therapeutic intervention(s).
- Total small bowel enteroscopy rate: Defined as complete evaluation of the small bowel either with a single approach or combined anterograde and retrograde approach (if complete small bowel enteroscopy is intended anyway (Committee et al. 2015; Gerson et al. 2015).
- Diagnostic Yield (i.e. diagnosis, that explains findings from previous imaging or establishes a new diagnosis, that could explain clinical symptoms, that indicated PSE)
- User feedback and judgment of handling characteristics and other aspects: User feedback and assessment of handling characteristics and other logistical aspects regarding:
 - Handling of PowerSpiral
 - Instrument insertion of PowerSpiral
 - Precision of positioning during therapy of PowerSpiral
 - Time needed for procedure of PowerSpiral
 - Staff and resource needed for procedure of PowerSpiral
- Serious adverse events (PS product related)
- Adverse events during enteroscopy procedure and adverse events (PS product related)

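### The protocol's SAE definition contradicts itself on events treated as an outpatient in the emergency department, and the primary endpoint rests on that definition

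*Protocol*

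**What the plan says.** CIP 11.1.3 lists what makes an event serious. Two of the criteria do not depend on where the patient is treated: "A life-threatening illness or injury, or" and "In medical or surgical intervention to prevent life threatening illness or injury or permanent impairment to a body structure or a body function". In-patient or prolonged hospitalization is a separate criterion.

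The guidance that follows opens a list with "The following events are not considered to be serious adverse events". Two of its bullets concern care without admission. One covers emergency-department care: "Outpatient treatment in the emergency department although the reason for which this treatment was instituted may be serious". The other covers short visits to a consultation, open-door clinic or day hospital, and does not mention how serious the event may be.

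SAP 2.4 makes SAEs the primary endpoint: "The rate of serious adverse events during and after enteroscopy will constitute the primary endpoint for this study". SAP 2.3 attaches the decision: "If the upper confidence limit will be 8% or less, non-inferiority will be concluded". SAP 3.7.1 repeats the rule for the core safety population. The SAP has no definition of seriousness of its own; SAP 3.4.3 only codes it as no or yes. CIP 11.1.3 therefore decides what is counted.

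**The concern.** The emergency-department bullet expressly allows for a serious reason and still excludes the event. Bleeding that is controlled urgently, to prevent a life-threatening course, without admission is an SAE under the criteria and not an SAE under the bullet. Two investigators could code the same event differently, and each could point to the text.

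The primary SAE rate carries the only decision rule in the SAP. A carve-out by place of treatment acts on it in one direction: it can remove events and cannot add any. It also lets local admission practice influence the endpoint across about 12 sites in several countries. An event classed as non-serious also falls outside the immediate reporting duty in CIP 11.3.1.

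**Working it through.** **1. The two rules side by side (CIP 11.1.3).**

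| Event | Under the criteria | Under the bullets |
|---|---|---|
| Life-threatening, treated as an outpatient in the emergency department | SAE | Not an SAE, although a serious reason is foreseen |
| Intervention to prevent life-threatening illness or permanent impairment, same setting | SAE | Not an SAE, same bullet |
| Either of these, handled in a brief consultation or day-hospital visit | SAE | Not an SAE, because the bullet has no qualifier |
| Meets no criterion, outpatient visit only | Not an SAE | Not an SAE |

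The rules conflict in the first three rows. The list's opening words are not tied to the hospitalization criterion. Neighbouring rules do carry limits: planned hospitalization is excluded only without serious deterioration, and planned admission only if the condition does not worsen. These two bullets carry none.

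**2. When such an event could arise.**
- V4 is completed before discharge (CIP 3.4.3), and AEs are scheduled for collection at V2, V3 and V4 (CIP Table 2). Events during the procedure or the hospital stay are not outpatient visits, so the bullets do not reach them.
- Between procedures a patient may be at home: "There are no predetermined time intervals between V1 and V2 or V2 and V3". V3 is optional and only part of the subjects have it (CIP 3.1.2).

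The window is therefore mainly the V2–V3 gap in patients who have a second procedure.

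**3. Reproducing the plan's own figures.** CIP 3.3.6 expects 245 evaluable patients from 260 enrolled. The exact 95% upper limit for x patients out of n is the 0.975 quantile of Beta(x + 1, n − x). At n = 245 all six intervals in CIP Table 1 reproduce to the printed decimal; for example, 10 patients give 2.0% to 7.4%.

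**4. Where the 8% rule turns.** Patients are counted, as in CIP Table 1.

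| n | Largest passing count | Upper limit | Next count | Upper limit |
|---|---|---|---|---|
| 245 | 11 (4.5%) | 7.89% | 12 | 8.40% |
| 260 | 12 (4.6%) | 7.92% | 13 | 8.40% |

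The trial summary speaks of 260 cases in the final analysis and CIP 3.3.6 of 245, so both are shown. In each case the margin is one patient.

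**5. Sensitivity to an assumed share.** Let f be the share of SAE patients whose only SAE is removed by the bullets. The documents give no value for f. With a true rate of 8%, the probability of passing is P(X ≤ c) for X ~ Binomial(n, 0.08 × (1 − f)), where c is 11 or 12.

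| f (assumed) | Counted rate | n = 245 | n = 260 |
|---|---|---|---|
| 0% | 8.00% | 2.2% | 2.3% |
| 1% | 7.92% | 2.4% | 2.5% |
| 2% | 7.84% | 2.7% | 2.8% |
| 5% | 7.60% | 3.6% | 3.8% |
| 10% | 7.20% | 5.8% | 6.1% |
| 20% | 6.40% | 13.5% | 14.6% |

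Given the narrow window in step 2, the lower rows are upper-end illustrations, not expectations.

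**The case against.** The best defence is that the bullets were meant only to explain the hospitalization criterion. All of them concern hospital contact: consultation or day hospital, emergency care without admission, and planned admission. Read that way, nothing serious is lost and only a clarifying phrase is missing. This is a plausible account of the intent, but the text does not say it, and the emergency-department bullet points the other way by allowing for a serious reason.

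The defence on size is stronger and largely stands. Participation lasts about 2 days to one week (CIP 3.3.5), V4 precedes discharge, and only some patients have a second procedure. Every AE is recorded whatever its seriousness (CIP 11.2.1). SAP 3.7.2 tabulates bleeding, perforation and pancreatitis as AEs of special interest, for all AEs as well as for SAEs. An excluded bleed would thus still be reported, though not in the primary rate.

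Three stronger readings are tempting, and the documents do not support them:

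- A reader might take the four weeks in CIP 11.2.1 as a post-discharge window in which many outpatient events would be lost. The sentence that follows it is about collecting further information needed to assess an event, so its most natural reading is follow-up of events already reported.
- A reader might infer that both bullets exclude events expressly despite a serious reason. Those words belong to the emergency-department bullet alone.
- A reader might conclude that the comparison with balloon-assisted enteroscopy is biased by a known amount. That depends on whether the 8% historical figure counted events treated without admission, which the documents do not say.

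**Conclusion.** The contradiction is in the text of CIP 11.1.3 and reaches the primary endpoint. Following the bullets can only lower the observed SAE rate, and so can only raise the chance of meeting the fixed 8% limit. Near the boundary a single reclassified patient reverses the conclusion: 11 against 12 at 245 patients, 12 against 13 at 260.

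The practical effect is probably small, because the exposure is mainly the V2–V3 gap in patients with a second procedure. It cannot be sized from the documents. If 1% to 2% of SAE patients were affected, the chance of passing at a true rate of 8% and 260 patients would move from 2.3% to 2.5%–2.8%. Shares of 10% or 20% would give 6.1% or 14.6%, but nothing in the plan supports shares that large. The calculation counts patients, as CIP Table 1 does; SAP 3.7.1 describes the numerator as a number of events. The finding is an unresolved wording conflict that is cheap to remove. It does not show that the rule was designed to hide serious events.

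**What to change.** Keep the bullets and reconcile them with the criteria in CIP 11.1.3. Suggested wording: *Outpatient, day-hospital or emergency-department treatment alone does not count as in-patient hospitalization; any event meeting a listed criterion is an SAE wherever it is treated.* Deleting the bullets is less sound, because they usefully say that a visit without admission does not by itself make an event serious.

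Carry the sentence into the CRF guidance, and have SAP 2.4 and 3.7.1 refer to the reconciled definition. AEs already recorded can be checked against it.

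The cost is one sentence in the CIP, matching CRF guidance and a cross-reference in the SAP. The downside is that the observed SAE rate may be slightly higher. If such events are rare, nothing is lost.
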